**TABLE 5: Visit 4 Procedures**

VISIT 4: FOLLOW-UP VISIT	
Component	Procedure/Analysis
ADMINISTRATIVE	

• Collect/Update Contact Information

• Visit Questionnaire

• Abstinence/Condom Counseling (& distribution prn)

• Assess/Document Adverse Events

• Participant Reimbursement

ACCEPTABILITY	

• Acceptability Questionnaire

URINE	

• Pregnancy test

• Urine dipstick, as clinically indicated

VAGINAL	

• pH

• Wet Mount, as clinically indicated

• Trichomonas (NAAT), as clinically indicated

• Gram Stain

• Quantitative Vaginal Culture

• Quantitative PCR for microbiota

• Future Use

CERVICAL	

• GC/CT (NAAT), as clinically indicated

• Future Use

CVL	

• Levels of antiviral activity

• Lectin microarray

• Levels of glycoproteins and mucins

• Levels of cytokines & innate immunity factors

• Eudragit® level

PHYSICAL EXAM	

• Physical Exam, as clinically indicated

• Vital Signs (BP)

PELVIC EXAM	

• Bimanual Exam, as clinically indicated

• External Genital & Speculum Exam

## 7.6 Participants Who Become Pregnant

Urine pregnancy tests will be performed at screening, enrollment, Visit 3, the last study visit, and as clinically indicated. Participants who become pregnant will be referred for care. Should the pregnancy be diagnosed during study follow-up, pelvic exams will only be performed to evaluate a participant's reported symptom. No genital specimens will be collected in a pregnant participant.

Of note, the participant will be encouraged to continue in the study so that safety data might be collected. Participants who are pregnant at the final study visit will be contacted after their study participation to ascertain the pregnancy outcome.

## 7.7 Interim Visits

Interim visits may be performed at any time during the study (and study procedures repeated as clinically indicated), for the following or other reasons:

- For administrative reasons, e.g., a participant may have questions for study staff, or may need to re-schedule a follow-up visit.

- In response to AEs. When interim contacts or visits are completed in response to participant reports of AEs, study staff will assess the reported event clinically and provide or refer the participant to appropriate medical care.
- In the event of laboratory processing issues (i.e. inconclusive STD testing, lost or inadequate sample
- For other reasons at participant request.

Details of the interim visit will be recorded in the chart notes.

## 7.8 Clinical Evaluations and Procedures

Physical exams will include the following assessments:

- Vital signs:
  - Blood pressure
- Measurements of:
  - Weight (at Screening only)
  - Height (at Screening only)
- Focused physical exam (at Screening only):
  - General appearance
  - Cardiac exam
  - Respiratory exam
  - Abdomen

Additional assessments may be performed at the discretion of the examining clinician in response to symptoms or illnesses present at the time of the exam.

## 7.9 Laboratory Evaluations

### Clinical Local Laboratory

Urine pregnancy test  
Rapid saliva HIV test  
Wet mount if clinically indicated  
Vaginal pH  
Dipstick urinalysis  
Confirmatory HIV testing if indicated

### MWRI Laboratories

Cervical NAAT for chlamydia, gonorrhea  
Vaginal NAAT for trichomonas  
Vaginal Gram stain  
Quantitative vaginal cultures  
Quantitative PCR for selected microbiota  
Levels of cytokines and innate immunity factors from CVL  
Anti-viral activity from CVL

### New York University Laboratory ([name]) and/or MWRI Laboratory

Levels of glycoproteins and mucin in CVL  
Lectin microarray in CVL

### University of Colorado Lab

### **7.10 Specimen Collection and Processing**

The site will adhere to the standards of good clinical laboratory practice and site standard operating procedures for proper collection, processing, labeling, handling, transport, and storage of specimens. In cases where laboratory results are not available due to administrative or laboratory error, sites are permitted to re-draw and/or re-collect specimens.

### **7.11 Biohazard Containment**

As the transmission of HIV and other blood-borne pathogens can occur through contact with contaminated needles, blood, and blood products, appropriate blood and secretion precautions will be employed by all personnel in the drawing of blood and shipping and handling of all specimens for this study as recommended by the CDC and NIH. All biological specimens sent to the University of Colorado lab will be transported using packaging mandated by CFR 42 Part 72. Biohazardous waste will be contained according to institutional, transportation/carrier, and all other applicable regulations.

## **8 ASSESSMENT OF SAFETY AND CLINICAL MANAGEMENT**

### **8.1 Safety Monitoring**

The study site investigators are responsible for continuous close safety monitoring of all study participants, and for alerting the Protocol Team if unexpected concerns arise. A sub-group of the Protocol Team, including the Protocol Chair or designee, the DAIDS Medical Officer, and the External Safety Monitor will serve as the Protocol Safety Review Team (PSRT). Close cooperation among the PSRT and the study site will be necessary to monitor participant safety and respond to occurrences of toxicity in a timely manner. Appropriate safety monitoring will be contingent upon excellent communication between study participants and study staff, and upon cooperation among study staff, investigators, the External Safety Monitor, and the DAIDS Medical Officer.

### **8.2 Clinical Data Safety Review**

An External Safety Monitor who is familiar with the pertinent scientific literature related to the study product will be responsible for the first review of data and safety monitoring. This physician, independent of the study sponsor, will be available to monitor data from this site. His/her minimum qualifications will include experience as a physician and experience in the conduct of clinical research. This individual will not receive salary or other support from the grant. The External (Independent) Safety Monitor model has been used successfully for other Magee-Womens Hospital Reproductive Infectious Disease studies involving investigational products. The proposed individual will meet the qualifications outlined above and have training in the importance of the objective treatment of clinical safety data.

The Data Management team for this site will generate data summaries for the Protocol Chair, the External Safety Monitor, and the DAIDS Medical Officer on an at least monthly basis. More frequent ad hoc safety reviews can be implemented during the initial enrollment and throughout the study as needed. These data summaries will include adverse event, accrual and retention data. The External Safety Monitor will evaluate adverse event data independently as well to determine whether the study protocol should continue as originally designed, should be changed, or should be terminated.

Approximately once a month the PSRT will convene via email or telephone to review adverse event data. Only masked safety data will be reviewed by the PSRT. If more urgent safety matters arise, telephone calls can occur more frequently.

The IRB will be notified of any serious and unexpected adverse events according to the policies outlined in the University of Pittsburgh IRB Policy and Procedure Manual.

The following information will be submitted to the University of Pittsburgh IRB at the time of renewal of a research protocol, as required by the IRB guidelines:

- The frequency of monitoring during the renewal interval, including the dates of data and safety monitoring;
- A summary of any assessment performed to evaluate external factors or other relevant information that may have an impact on the safety of study volunteers or the ethics of the research study;
- A summary of the outcome of procedural reviews conducted to ensure subject privacy and research data confidentiality;
- Any conclusions regarding changes to the anticipated benefit-to-risk ratio of study participation and final recommendations related to continuing, changing, or terminating the study, with accompanying rationales as appropriate.

### **8.3 Adverse Events Definitions**

An AE is defined as any untoward medical occurrence in a clinical research participant administered an investigational product and which does not necessarily have a causal relationship with the investigational product. As such, an AE can be an unfavorable or unintended sign (including an abnormal laboratory finding, for example), symptom or disease temporally associated with the use of an investigational product, whether or not considered related to the product. This definition is applied to all groups beginning from the time of randomization.

Study participants will be provided instructions for contacting the study site to report any untoward medical occurrences they may experience, except for possible life-threatening events, for which they will be instructed to seek immediate emergency care. Where feasible and medically appropriate, participants will be encouraged to seek evaluation at Magee-Womens Hospital of UPMC, where the study clinicians are based, and to request that a study clinician be contacted upon their arrival. All participants reporting a clinically significant untoward medical occurrence will be followed either in person or by phone until the occurrence resolves (returns to baseline) or stabilizes over a four week period.

Study site staff will document in source documents all AEs reported by or observed in enrolled study participants regardless of severity and presumed relationship to study product.

For each study participant, AE documentation and reporting will be undertaken throughout the scheduled duration of follow-up, i.e., through Visit 4.

The PI/designee will grade the severity of each AE and the relationship of the AE to study product:

AE severity will be graded per the DAIDS Table for Grading Adult and Pediatric Adverse Events, Version 2.1, July 2017 and the Female Genital Grading Table for Use in Microbicide Studies (Appendix 1, version 1.0, November 2007) except that asymptomatic BV will not be considered an AE. AEs not included in the Female Genital Grading Table will be graded by the DAIDS AE Grading Table Version 2.1, July 2017. In cases where a genital AE is covered in both tables, the Female Genital Grading Table for Use in Microbicide Studies will be the grading scale utilized.

The relationship of all reported AEs will be assessed based on the Manual for Expedited Reporting of Adverse Events to DAIDS (Version 2.0, dated January 2010) and the clinical judgment of the PI/designee.

Per the Manual for Expedited Reporting of Adverse Events to DAIDS, the relationship categories that will be used for this study are:

*Related:* There is a reasonable possibility that the AE may be related to the study agent(s)

*Not related:* There is not a reasonable possibility that the AE is related to the study agent(s)  
The study products that must be considered when AE relationships are assigned are the placebo film.

The DAIDS Table for Grading Adult and Pediatric Adverse Events, the Female Genital Grading Table for Use in Microbicide Studies, and Version 2.0 of the Manual for Expedited Reporting of Adverse Events to DAIDS are available on the DAIDS Regulatory Support Center (RSC) web site: <http://rsc.tech-res.com/>

All AEs will be captured on an AE log form. The form should be reviewed at each study visit and updated as needed. For any serious or expedited AEs (SAEs/EAEs) that are continuing at

a participant's study exit visit, the PI/designee must establish a clinically appropriate follow-up plan for the AE and review with the DAIDS Medical Officer. At a minimum, the AE must be re-assessed by study staff at least 2 weeks after the participant's study exit visit (Visit 4); additional evaluations also may take place at the discretion of the PI/designee. The same approach must be taken for any AEs deemed related to study product that are found to have increased in severity at the study exit visit (Visit 4). For those AEs requiring re-assessment, if the AE has not resolved or stabilized at the time of re-assessment, study staff will continue to re-assess the participant at least once per month while the study is ongoing. After the study has ended, all AEs requiring re-assessment will be re-assessed at least once within the 30-60 days after the study end date.

## **8.4 Expedited Adverse Event Reporting Requirements**

### **8.4.1 Expedited Adverse Event Reporting to DAIDS**

Requirements, definitions and methods for expedited reporting of Adverse Events (AEs) are outlined in Version 2.0 of the DAIDS EAE Manual, which is available on the DAIDS RSC website at <http://rsc.tech-res.com/clinical-research-sites/safety-reporting/manual>.

The DAIDS Adverse Experience Reporting System (DAERS), an internet-based reporting system, must be used for expedited AE reporting to DAIDS. In the event of system outages or technical difficulties, expedited AEs may be submitted via the DAIDS EAE Form. This form is available on the DAIDS RSC website at <http://rsc.tech-res.com/clinical-research-sites/safety-reporting/daids/paper-eae-reporting>.

For questions about DAERS, please contact NIAID CRMS Support at [[contact]](mailto:[contact]). Please note that site queries may also be sent from within the DAERS application itself.

For questions about expedited reporting, please contact the DAIDS RSC Safety Office at [[contact]](mailto:[contact]).

EAE reporting procedures specific to this protocol are that once the site has submitted EAEs via DAERS (as above), the RSC Safety Office will also prepare the draft safety reports and send them to the DAIDS Medical Officers for review. The study site will be contacted by the DAIDS Medical Officer if any further information or clarification is needed after the report is evaluated.

For all EAEs submitted, sites must file an RSC update with the final or stable outcome unless the initial EAE submitted had a final or stable outcome noted already.

#### EAE Reporting Level

This study uses SAE category of expedited AE reporting as defined in the DAIDS EAE Manual.

#### Study Agents for Expedited Reporting to DAIDS

The study agent that must be considered in determining relationships of AEs requiring expedited reporting to DAIDS is the placebo film.

#### Reporting Period

AEs must be reported on an expedited basis during the entire study duration for an individual subject (from study enrollment until study completion or discontinuation of the subject from study participation for any reason). After the protocol-defined AE reporting period, unless otherwise noted, only suspected unexpected serious adverse reactions (SUSARs as defined in Version 2.0 of the EAE Manual) will be reported to DAIDS if the study staff become aware of the events on a passive basis (from publicly available information).

#### **8.4.2 Reporting of Critical Events to DAIDS**

Protocol violations and unanticipated problems must be reported to DAIDS as critical events. The following information about the critical event will be submitted to DAIDS MO and Clinical Operations Officer:

A detailed description of the problem;

Actions the study site is taking or plans to take to address the problem, such as suspending participant enrollment, termination of research, revising study protocol or informed consent documents, increasing monitoring of the study participant, etc. Any revisions to the study protocol and informed consent must be reviewed and approved by the DAIDS MO and study site IRB prior to implementation.

Serious or continuing noncompliance and suspension/termination of IRB approval must be reported as critical events as well.

#### **8.5 Clinical Management of Adverse Events**

By definition, an adverse event can be either new finding or symptom or a worsening of a pre-existing condition. In order to accurately capture adverse events in follow-up, a thorough baseline history will be obtained at Visit 1 and Visit 2. For example, for participants who endorse a history of headache, site staff will probe for and record details surrounding the condition such as frequency, location, duration, medication use, triggers, etc. Only by eliciting a full description will study staff be equipped to determine whether a subsequent event in follow-up is a clinically distinct event or not.

Adverse events will be elicited at each follow-up visit. Referral to appropriate care will be offered to participants as needed. Vaginitis and some sexually transmitted infections can be treated in the study clinic. The PI/designee should manage STI/RTI per CDC guidelines, available at <http://www.cdc.gov>. Observed single dose treatment should be provided whenever possible. Vaginally applied medications should not be used if possible.

##### **8.5.1 Product Hold**

In the unlikely event that a participant is intolerant of the study product immediately after placement, the site clinician will perform a pelvic exam to remove all visible product.

#### **8.6 Criteria for Early Termination of Study Participation**

Participants may voluntarily withdraw from the study for any reason at any time. The Site PI/designee also may withdraw participants from the study to protect their safety and/or if they are unwilling or unable to comply with required study procedures. Participants also may be withdrawn if the study sponsors, government or regulatory authorities, including the Office of Human Research Protections (OHRP), or site IRBs/ECs terminate the study prior to its planned end date. Every reasonable effort is made to complete a final evaluation of participants who withdraw or are withdrawn from the study prior to completing follow-up. Study staff members will record the reason(s) for all withdrawals in participants' study records.

## 9 STATISTICAL CONSIDERATIONS

### 9.1 Review of Study Design

The primary aim of this study is to assess the safety of a single dose of placebo film. Urogenital, systemic and menstrual symptoms will be collected via symptom review with participants. Testing for sexually transmitted infections and vaginitis will occur at the screening visit to rule out other potential causes of reproductive tract inflammation and epithelial disruption. This testing will be repeated during subsequent examinations if clinically indicated. Data on epithelial inflammation and disruption will be collected during visual examination of the reproductive tract. Pharmacokinetic measures will assess persistence following a single exposure.

### 9.2 Sample Size and Accrual

The primary aim of the study is to assess the local and systemic safety of a single dose of placebo vaginal film. The primary endpoint is the proportion of participants who experience a Grade 2 or higher adverse event. The proposed total sample size is N=64 divided into 4 arms (placebo film with follow up at days 3, 7, 10, or 14 assigned at a 1:1:1:1 ratio). Based on previous studies of vaginal products conducted at the study site, the accrual of 64 eligible subjects with normal reproductive tracts is expected to require the screening of approximately 150 volunteers. Since unevaluable participants will be replaced, it is anticipated that 64 women exposed to study product will complete study visit 3.

The sample size is based on the exact binomial probability of observing at least two Grade 2 or higher Adverse Events. For a given arm, if the true rate of a given toxicity endpoint is 5%, 16 women per arm provide 80% power to exclude toxicity endpoint rates greater than 27% (the probability of observing zero or one event is less than 0.05 when the true rate is 27%).

Table 6: Power Calculations for FAME 101

Event Rate	P(No events   n=16)	P(1 or more events   n=16)	P(2 or more events   n=16)
1%	0.851	0.149	0.011
5%	0.440	0.560	0.189
10%	0.185	0.815	0.485
15%	0.074	0.926	0.716
20%	0.028	0.972	0.859
25%	0.010	0.990	0.937
27%	0.007	0.993	0.955
30%	0.003	0.997	0.974
35%	0.001	0.999	0.990

In previous studies of two different placebo film products the combined frequency of Grade 2 or higher Adverse Events was 19%. Assuming a similar frequency in the current study, a sample size of 64 women will assure that a 95% confidence interval for the Grade 2 or higher Adverse Events rate has an upper limit of no greater than 30%.

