### **9.5 Random Assignment**

The randomization scheme will be generated and maintained by a member of the Data Management Division at the study site. Women will be randomized to one of the four arms at a 1:1:1:1 ratio using a permuted block design with random block sizes of 4 and 8. In order to minimize bias in group assignment, participants will be given study identification numbers. A study staff member will allot the identification numbers in sequential order as participants become eligible to enroll in the study. These numbers will be randomly assigned with timing of Visit 3. The randomization scheme will be created for a total of 72 participants; the overage will be created to compensate for participant withdrawals or unusable products.

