### **9.6.2 Primary Endpoint Analysis**

The number of adverse events will be summarized by severity, body system, and relationship to study product using frequencies, percent, and 95% confidence intervals. Individual participants will contribute once to the calculation of event rates.

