#### **9.6.4 Analysis Cohort**

The cohort will be defined as participants who are randomized. It will be used for analyses of baseline characteristics, protocol deviations and violations, and trial conduct. The intent-to-treat cohort (ITT) will be defined as those who were randomized. The evaluable cohort (Eval) is a subset of ITT participants. Evaluable participants will be defined as participants who complete the Screening and Enrollment Visits and return for their Visit 3 within the window. Non-evaluable participants will be replaced.

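### Section 9.2 says 64 women assure a 95% upper limit of at most 30% for the Grade 2+ AE rate; at a true rate of 19% that is met in only about 43–56% of trials

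*Combined protocol and SAP*

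**What the plan says.** Section 9.2 (Sample Size and Accrual) makes two separate statements about sample size.

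- The first is per arm. It says "The sample size is based on the exact binomial probability of observing at least two Grade 2 or higher Adverse Events" and works with 16 women per arm, a true rate of 5%, and exclusion of rates above 27%.
- The second covers the whole sample: "The proposed total sample size is N=64 divided into 4 arms". It begins from earlier data: "In previous studies of two different placebo film products the combined frequency of Grade 2 or higher Adverse Events was 19"%. It then supposes a similar frequency in this trial and concludes that "a sample size of 64 women will assure that a 95% confidence interval for the Grade 2 or higher Adverse Events rate" will be capped: the interval, it says, "has an upper limit of no greater than 30"%.

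The second statement gives no probability of meeting the limit, names no interval method, and does not say whether 19% stands for the true rate or for the frequency that will be observed.

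The analysis sections do not settle this. Section 9.6.2 summarises AEs by severity, body system and "relationship to study product using frequencies, percent, and 95% confidence intervals", with each woman counted once. Table 7 lists the same statistics. Neither names a method for the interval.

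**The concern.** To assure an upper limit is to promise something about a random quantity. The upper limit depends on how many of the 64 women have an event, and that number varies from trial to trial even when the underlying rate is exactly 19%. A limit calculated at the expected count will be exceeded in a large share of trials, and here the expected count lies right at the edge.

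The primary objective is safety and the planned primary analysis is estimation with confidence intervals. This sentence is the only precision statement for the full sample, and the only one built on the AE rate seen with earlier placebo films (the per-arm power statement assumes 5%). A reader who accepts it could take a reported upper limit of 31% or 32% as a warning sign or a failed design assumption, when it would be an ordinary result for a film that behaves just like its predecessors.

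**Working it through.** **Inputs.** n = 64, frequency 19% and target limit 30% are from 9.2. One contribution per woman and a 95% level are from 9.6.2, so the count X is treated as binomial. Two-sided intervals are assumed, as is usual for a 95% confidence interval. Because the method is not named, six are shown.

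**Step 1: reproduce the plan's figure.** 0.19 × 64 = 12.16, so the nearest count is 12 (12/64 = 18.75%). Two examples:

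- Wald: p + 1.96·√(p(1−p)/n) = 0.1875 + 1.96·√(0.1875 × 0.8125/64) = 0.1875 + 0.0956 = 0.283.
- Exact (Clopper-Pearson): the 97.5% quantile of Beta(x+1, n−x) = Beta(13, 52), which is 0.3046. The lower limit is 0.1008.

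Two-sided 95% upper limits:

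| Method | 12/64 | 13/64 |
|---|---|---|
| Wald | 28.3% | 30.2% |
| Jeffreys | 29.6% | 31.3% |
| Mid-P | 29.7% | 31.5% |
| Wilson | 29.97% | 31.7% |
| Agresti-Coull | 30.1% | 31.9% |
| Exact | 30.5% | 32.2% |

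The plan's 30% therefore reproduces, approximately, as the limit when 12 of 64 women have an event. Four methods meet it and two narrowly miss. With one more event all six miss.

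**Step 2: probability of meeting 30% when the true rate is 19%.** For each method, take the largest count whose upper limit is at most 30%, then P(X ≤ that count) for X ~ Binomial(64, 0.19).

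- Exact and Agresti-Coull need 11 or fewer events: P(X ≤ 11) = 0.429.
- Wald, Wilson, Jeffreys and mid-P need 12 or fewer: P(X ≤ 12) = 0.556.

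The limit is missed in 1 − 0.556 = 44% to 1 − 0.429 = 57% of trials.

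**Step 3: other true rates.** The plan says only that the frequency is similar, so this range is an assumption.

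| True rate | P(X ≤ 11) | P(X ≤ 12) |
|---|---|---|
| 15% | 0.754 | 0.845 |
| 17% | 0.595 | 0.714 |
| 19% | 0.429 | 0.556 |
| 21% | 0.283 | 0.397 |
| 23% | 0.170 | 0.260 |

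An 80% chance of meeting 30% requires a true rate of at most 14.3% (11 or fewer events) or 15.8% (12 or fewer).

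**Step 4: does over-enrolment rescue it?** Section 9.5 says "The randomization scheme will be created for a total of 72 participants", and 9.6.4 says "The intent-to-treat cohort (ITT) will be defined as those who were randomized". If all 72 slots were filled and all 72 women analysed, the exact, Agresti-Coull and Wilson intervals need 13 or fewer events (P = 0.491 at 19%). Wald, Jeffreys and mid-P need 14 or fewer (P = 0.608).

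**Step 5: what N = 64 does support.** At a true 19%, P(X ≤ 14) is about 0.78, just short of 80%, and P(X ≤ 15) = 0.856. The exact upper limit at 15/64 is 35.7%. That is the exact limit that holds with at least 80% probability.

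**The case against.** The strongest reply is about reading. Section 9.2 speaks of a true rate in its per-arm calculation but of a frequency in this sentence, the same word it uses for what the earlier studies observed. Read as an observed frequency, the sentence is an ordinary expected-precision statement, and 30% is right for four of the six methods and for all six after rounding to a whole percent. This stands as far as it goes: 30% is not a miscalculation of the expected limit. It does not save the sentence, because a sample size cannot assure an observed count, and one event above 12 breaks the limit under every two-sided method tried.

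Rounding and one-sided bounds can also be tried.

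- Rounded to whole percents, 12 events pass under every method (P = 0.556) and 13 pass under Wald only (P = 0.675).
- A one-sided 95% exact bound at 13/64 is 30.3%, which leaves P = 0.556. One-sided Wilson (29.7%) and Wald (28.6%) bounds admit 13 events, giving P = 0.675.

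So the 43–56% range applies to unrounded two-sided intervals. The most favourable of these alternatives at N = 64 still fails about one trial in three.

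Finally, little hangs on the sentence. The stated basis for N is the per-arm calculation, which reproduces under the one-sided 5% rule it states: P(0 or 1 event in 16) = 0.811 at 5% and 0.045 at 27%. No success or stopping criterion uses 30%. That limits the importance of the point but does not make the statement correct. It is also fair to say that 80% assurance and the exact method are choices. The plan sets neither for this interval, though 9.2 uses exact binomial probabilities elsewhere.

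**Conclusion.** The concern holds. With 64 women and a true Grade 2+ AE rate of 19%, a two-sided 95% upper limit of at most 30% is reached in 43% of trials (exact, Agresti-Coull) or 56% (Wald, Wilson, Jeffreys, mid-P). Under the observed-frequency reading the sentence describes essentially one count, 12/64, and is true or false according to a method the plan does not name; by the exact interval that count gives 30.5%. This rests on binomial sampling with each woman counted once, two-sided unrounded limits, and 64 women analysed. Relaxing the last two, or using one-sided bounds, does not bring the probability near assurance. The sentence should be corrected, but the practical impact is modest because no decision depends on the 30%.

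**What to change.** Replace the last sentence of 9.2 with wording such as: *If 12 of 64 women have a Grade 2 or higher AE, the exact 95% confidence interval is 10.1% to 30.5%. If the true rate is 19%, the exact upper limit will be at most about 36% with at least 80% probability (15 or fewer events, P = 0.86).* In 9.6.2, state that the intervals for AE proportions are exact (Clopper-Pearson), so that the planned precision and the reported interval use the same method. If another method or assurance level is preferred, name it and recompute both figures.

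Only if the per-arm 27% claim is carried into reporting, give the matching one-sided 95% exact upper bound as well (26.4% for 1/16).

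The cost is one sentence in 9.2 and one phrase in 9.6.2. The stated bound becomes less favourable, about 36% instead of 30%. No participants are added and the design does not change.
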